Evidence from human intervention trials and mechanistic studies suggests that tomato and tomato based products are associated with a reduction in CVD risk. The mechanism by which this protective effect occurs is not clearly understood but research has focused on its potential to modulate platelet function. In a single-blind, randomized, parallel design human intervention trial (3-groups), we aim to recruit 99 participants (33/group) to ingest an orange flavoured beverage containing different doses of a tomato pomace extract (1.0 and 2.5 g,) or placebo control over a 5-day period. The acute and longer term effects of the treatments on platelet aggregation will be evaluated at the start and end of the intervention period. Before implementing this large scale human intervention trial we will also conduct a preliminary 'ascending dose human tolerance study' in a small group of participants across a \sim 3 week period.

[name] is Chief Investigator (CI) for this trial. The trial will be conducted at the University of Talca by [name] (Research nurse), [name] (CI; Researcher), [name] (Researcher) and other members of the research group may be required to assist. Statistical analysis of the data will be undertaken by [name] (statistician; Institute of Food Research, UK). Tomato pomace will be processed and supplied by Centro de Estudios en Alimentos Procesados (CEAP). This study is funded by the Newton Picarte Fund. This fund supports joint projects between Chilean and British researchers.

2. Scientific Background

Epidemiological evidence supports the concept that a diet rich in fruit and vegetables affords protection against the onset of cardiovascular disease (CVD) [1]. The aetiology of CVD is multi-factorial, but it has been recognized for some time that platelet function is related to the risk of developing atherosclerosis [2], a precursor to CVD. Activated platelets play a key role in the development of atherosclerosis by contributing to plaque formation within blood vessels during the early stages of atherogenesis. Platelets become activated after binding with von Willibrand (vWF) factor and collagen, which are secreted in response to damaged endothelial cells [3]. Subsequently, collagen and vWF bind to glycoprotein receptors (GPIIb/IIIa complex) situated on the platelet surface [4]. The activated platelets in turn synthesize and secrete thromboxane A₂ and intracellular ADP which, combined with conformational changes in the glycoprotein complex, result in platelet aggregation. Platelet hyperaggregation is known to be apparent in disease states such as CVD and several antiplatelet therapies such as aspirin and glycoprotein IIb/IIIa inhibitors significantly reduce the incidence of coronary events [5]. In addition, healthy people (middle aged and older) and people under stress can also display impaired platelet activity. Optimal platelet function is therefore an important tool in the prevention of CVD and dietary solutions may be considered as one approach to maintaining cardiovascular health.

Tomatoes and tomato based products are a rich dietary source of vitamins (C & E), carotenoids (β -carotene, lycopene), polyphenols (naringenin, quercetin, kaempferol) and folates. Evidence from human intervention trials and mechanistic studies suggest that tomato and tomato based products are associated with a reduction in CVD risk.

Whilst some reports have attributed these beneficial effects to lycopene [6, 7], others report that lycopene may not be associated with CVD risk [8, 9], indicating that other components of tomato may be responsible for the cardio-protective effects observed. The cardio-protective properties of tomatoes and tomato based products in humans include the ability to improve lipid profiles [10-12] as well as induce anti-inflammatory [12] and anti-platelet activities [13, 14].

Industrial processing of tomatoes into sauces, purees, pastes and juices result in the accumulation of tomato by-products, or pomace. Historically, tomato pomace has been viewed as a waste product and is either disposed of or used as animal feed. The tomato pomace is about 5% of the processed tomato (by weight) and consists of tomato peel and pulp (78%) and crushed seeds (22%). The tomato pomace is composed of fibre (60%), sugar (27%), protein (19%), pectin (8%), fat (6%) and minerals (4%). Research already conducted at the University of Talca evaluating the *in vitro*, *ex vivo* and *In vivo* effects of aqueous extracts of fresh tomatoes and tomato pomace on platelet function, has demonstrated marked decreases in platelet aggregation [15-17]. Moreover, the inhibitory effect on platelet aggregation was shown to be greater in tomato pomace extracts when compared with fresh tomato extracts [15, 17]. This is an important finding because the data indicate that industrial processing of tomato into pomace, may not adversely affect the anti-platelet activity observed in other studies and may therefore, be an important tool in the prevention of CVD.

It is our intention to investigate the acute and longer term effects of ingesting tomato pomace extracts on platelet function in humans. Since the tomato pomace extract is not ordinarily consumed by the wider population in this processed format, we firstly propose to conduct a preliminary ascending dose human tolerance study in a small group of people. In short, the purpose of this submission is to seek ethical approval to conduct a two phase study.

- Phase 1: A preliminary 'ascending dose' human tolerance study of ingesting a tomato pomace extract; leading onto
- Phase 2: A single-blind, randomized, parallel design, human intervention trial to investigate the effects of ingesting different doses of the tomato pomace extract on platelet aggregation.

Each phase of the study is described in detail below.

3. PHASE 1 – Ascending dose human tolerance study of a tomato pomace extract

3.1 Study objectives

The objective of this single ascending dose study is to assess the safety and tolerability of the ingestion of tomato pomace extracts in humans.

3.2 Study Design

Male participants (n=15) will be recruited to ingest a tomato pomace extract once daily for 5-days across three different doses. In week one, five participants will ingest 1.0 g of extract per day for 5 days. In week two, the next five participants will ingest 2.5 g of extract per day, for five days. In week three, the next five participants will ingest 10 g extract per day, for five days. The 1.0 and 2.5 g doses of extract are the same doses we intend to investigate in phase 2. Tolerability of the tomato pomace ingestion will be assessed by physical measurements (blood pressure and pulse rate) and a gastro-intestinal well-being assessment before ingestion, and then again

3-h after ingestion of the tomato pomace extract on each of the 5 treatment days. The blood test for full blood count and biochemical profile undertaken at clinical screening (section 3.6) will form part of the baseline assessment profile. The same blood tests will be repeated 24-h after the last treatment on day 5. Figure 1 is a schematic overview of the study.

Eligibili asses	sment I	Day 1 Day 2	Day 3	Day 4	Day	5 Day 6
	Maximum 2-weeks					
		t= 0-h; Blood p intestina	oressure, pulse al well-being qu		8	
Consent Health questionnaire		Ingestio	n of treatment	dose.		
		t=3-h; Blood pressure, pulse rate, gastro- intestinal well-being questionnaire				Blood pressure, pulse rate, gastro-intestinal well being questionnal
Blood pressure, pulse, height, weight		intestin	ar weir being q	acodonnanc		5 ,
						Fasted blood sample
-						(Full blood count and
	ed blood sample					biochemical profile)
	blood count and hemical profile)					

Figure 1. Schematic overview of phase 1

- 3.3 Inclusion criteria
 - Apparently healthy men aged between 18 and 26 years
 - BMI >19.5 and < 26.0
- 3.4 Exclusion criteria
 - Known tomato allergy
 - Chronic medical conditions requiring active treatment (e.g. Cardiovascular disease, diabetes, asthma)
 - Medically or self-prescribed medication
 - Kidney or liver disease/disorders
 - Gastro-intestinal disease/disorders
 - Smokers
 - Parallel participation in another research project which involves dietary intervention
 - Depressed or elevated blood pressure measurements (<90/50 or 95/55 if symptomatic or ≥160/100 (mmHg)
 - Any person related to or living with any member of the study team

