4.5 Exclusion criteria

•Known tomato allergy

- •Chronic medical conditions requiring active treatment (e.g. cardiovascular disease, diabetes, asthma)
- Gastro-intestinal disease/disorders
- Smokers
- Medically prescribed medication known to affect platelet function
- Self-prescribed medication known to affect platelet function (e.g. aspirin and non-steroidal anti-inflammatory drugs) unless participant is willing to give up.
- Bleeding disorders (e.g. haemophilia)
- Dietary supplements judged to affect study outcome
- Parallel participation in another research project which involves dietary intervention
- Blood donation within 16 weeks prior to the study
- Depressed or elevated blood pressure measurements (<90/50 or 95/50 if symptomatic or ≥ 160/100 mmHg)
- Any person related to or living with any member of the study team

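### Phase 1 has no bleeding-disorder exclusion, although Phase 2 has one and Phase 1 reaches four times the highest Phase 2 dose of an extract expected to inhibit platelets

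*Combined protocol and SAP*

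**What the plan says.** Phase 1 is the tolerability study. Its objective in section 3.1 is "to assess the safety and tolerability of the ingestion of tomato pomace extracts in humans". Section 3.2 sets three cohorts of five men, at 1.0, 2.5 and 10 g/day for five days: "In week three, the next five participants will ingest 10 g extract per day, for five days". Of the lower two doses it says: "The 1.0 and 2.5 g doses of extract are the same doses we intend to investigate in phase 2". The highest Phase 2 dose is therefore 2.5 g/day.

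The Scientific Background (section 2) reports that the group's work on aqueous extracts of fresh tomato and of pomace "has demonstrated marked decreases in platelet aggregation", with greater inhibition from pomace than from fresh tomato.

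Section 3.4 lists the Phase 1 exclusions. The one closest to this point is "Chronic medical conditions requiring active treatment (e.g. Cardiovascular disease, diabetes, asthma". Bleeding disorders are not named. Section 4.5 has essentially the same chronic-condition criterion for Phase 2 and, as a separate entry, "Bleeding disorders (e.g. haemophilia". No reason for the difference is given.

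Screening in section 3.6 consists of a health questionnaire (Annex 4), blood pressure, pulse, height and weight, a full blood count and a listed biochemical profile. Section 4.7 uses the same screening for Phase 2 and adds only a platelet aggregation test.

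**The concern.** The protocol applies a bleeding-disorder exclusion at the lower doses and not at the highest one. If the exclusion is there because the extract is expected to reduce platelet aggregation, that reason applies at least as strongly in Phase 1, which is where tolerability of the extract is first tested and where the only objective is safety.

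What is at stake is who may be dosed under the plan as written. Section 3.10 randomises men to dose once all 15 have been recruited, so section 3.4 has to be adequate for 10 g/day for every man enrolled. A bleed that led to hospital admission would also meet the definition of a serious adverse event in section 5.1, which then requires the trial to be suspended or terminated. The documents give no basis for saying how likely that is.

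**Working it through.** The plan has no calculated figure on this point, and its sample size (33 per group in Phase 2) is not affected. The check is a dose ratio and a comparison of the two sets of criteria.

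**Dose ratio.** Inputs: the highest Phase 1 dose is 10 g/day for five days (section 3.2); Phase 2 doses are 1.0 and 2.5 g/day for five days (section 4.3).

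- Highest Phase 1 dose / highest Phase 2 dose = 10 / 2.5 = 4.
- Highest Phase 1 dose / lowest Phase 2 dose = 10 / 1.0 = 10.
- Both phases dose for five days, so the ratios for total intake are the same: 50 g against 12.5 g, and 50 g against 5 g.

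**Criteria side by side.**

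| Item | Phase 1 (3.3, 3.4, 3.6) | Phase 2 (4.4, 4.5, 4.7) |
|---|---|---|
| Apparently healthy men, 18 to 26 | Required | Required |
| Chronic condition under active treatment | Excluded | Excluded |
| Bleeding disorder | Not listed | Excluded |
| Medication | All excluded, prescribed or not | Only platelet-active drugs; self-medicating men may enter if they agree to stop |
| Kidney or liver disease | Excluded | Not listed |
| Blood count and biochemistry | Must be normal | Same screening |
| Clotting test | None listed | None listed |
| Platelet aggregation | Not measured | Measured; at least 65% required |
| Highest dose | 10 g/day | 2.5 g/day |

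**Do the other Phase 1 entries cover the gap?** Take a man who knows he has a mild bleeding disorder and needs no treatment for it.

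1. The chronic-condition criterion turns on active treatment, so it does not exclude him.
2. He takes no medication, so that criterion does not exclude him.
3. A full blood count gives the number of platelets, not their function, and the listed biochemistry contains no clotting test. Both can be normal.
4. The doctor's power to exclude in section 3.6 is tied to the blood results, not to history.
5. The general health requirement, the chronic-condition criterion and the blood tests all apply in Phase 2 as well, and section 4.5 still lists bleeding disorders separately. The protocol itself does not treat those three as sufficient.

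This man is barred from 1.0 g/day by section 4.5 and is not barred from 10 g/day by section 3.4.

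**The case against.** The strongest reply is that the lists differ in both directions. Phase 1 bars all medication, which includes aspirin and other anti-inflammatory drugs, while Phase 2 admits users who agree to stop. Phase 1 also bars kidney and liver disease. This stands. A reader might infer that Phase 1 has the weaker bleeding screen overall, and the documents do not support that. The gap concerns bleeding disorders only.

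A reader might also count the Phase 2 entry "Dietary supplements judged to affect study outcome" as a second missing bleeding precaution. Its wording concerns the study outcome, which in Phase 2 is platelet aggregation (section 4.14). Phase 1 has no platelet outcome, so the omission there is not shown to be a safety gap. Likewise, the 65% aggregation threshold is an inclusion criterion with no stated safety purpose.

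Thirdly, Annex 4 may already ask about bleeding. Section 4.7 says that Phase 2 screening follows section 3.6 with one addition, which suggests that one questionnaire serves both phases. That is possible and cannot be checked here. It does not settle the matter: section 3.6 uses the questionnaire to apply the listed criteria, and section 3.4 lists no bleeding criterion to apply.

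Finally, the remaining group is small, and the background section reports reduced aggregation, not bleeding. Both statements are fair. They limit the size of the point without explaining the difference between the lists.

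**Conclusion.** The point holds in a narrow form. Section 3.4 omits the bleeding-disorder exclusion that section 4.5 contains, in the phase whose highest dose is 4 times that of Phase 2, and no other Phase 1 entry takes its place. The practical consequence is that a man with a known, mild, untreated bleeding disorder could be given 10 g/day in Phase 1 although he would be refused 1.0 g/day in Phase 2.

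This assumes that section 3.4 is the full list of Phase 1 exclusions and that Annex 4 does not work as an additional, unlisted criterion. It does not extend to a disorder that nobody knows about. A reader might infer that aligning the lists would prevent a bleed in such a man, but an exclusion line applied by interview cannot find him, and section 4.5 has the same limit. The number of men affected is probably very small, and the documents give no probability of a bleed. The case for a change rests on the unexplained difference, the safety purpose of Phase 1 and the very low cost.

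**What to change.** Reconcile sections 3.4 and 4.5 on the bleeding-disorder exclusion before Phase 1 starts, or state in the protocol why the two phases differ. Confirm that the Phase 1 health questionnaire (Annex 4) asks about bleeding history, and add the question if it does not.

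The cost is one line in section 3.4 and at most one question at an interview that already takes place, with possibly a very few volunteers lost. No test, visit or sample-size change is needed. If ethical approval has already been given, section 5.7 requires the change to be approved as an amendment first.

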3.5 Recruitment strategy

The study population will comprise apparently healthy men aged 18 - 26 years. A total of 15 participants are required to complete this phase of the study.

Recruitment of participants to this study will be achieved through poster and E-mail advertisements (annex 1) placed across the University of Talca, inviting anyone who is interested in receiving information about the study to contact named researchers. Those expressing an interest will be provided with a participant information sheet (annex 2). After reading the information sheet, those wishing to take part in the study will be invited to the research facility for an informal meeting with a member of the research team who will explain the study fully, focusing on the participant's

involvement. Participants will be encouraged to ask questions at this stage prior to making any commitment. At the end of the meeting, participants will be given ample opportunity to consider whether they wish to take part in the study. If, following the consideration period they wish to participate in the study, they will be asked to contact a member of the research team to arrange an appointment at the research facility for the pre-study clinical screening.

3.6 Clinical screening

Participants will attend the research facility following a 10-hour overnight fast but will be advised that they should drink water during the fasting period. On arrival at the research facility a member of the research team will go through the consent form (annex 3) with the participant and answer any questions that may arise at this stage. He will then be asked to sign a consent form agreeing to participate in the study. A copy of this form will be given to the participant to keep. A research nurse will then complete a basic health screening questionnaire (annex 4), measure and record blood pressure, pulse, height and weight and calculate body mass index. A 10 mL blood sample will be obtained for full blood count (hemogram) and biochemical profile. The biochemical profile will include: glucose, urea nitrogen, urea, total cholesterol, uric acid, total proteins, albumin, globulins, total bilirubin, transaminase GOT, GPT transaminase, GGT, lactate dehydrogenase, alkaline phosphatase, total calcium and phosphorous. The results of the full blood count and biochemical profile will be reviewed by a medical doctor ([name] MD and personnel of the Laboratorio Talca, Centro Diagnóstico Diagonal). In the event that the medical doctor deems the results of the blood test to be indicative of a health problem (that may compromise the well-being of the participant should he take part), then he will be excluded from the study. In these circumstances, the participant will be advised to contact a medical practitioner of his choice for further treatment/investigation.

Those participants meeting the basic inclusion/exclusion criteria (assessed using the health screening questionnaire) and with normal results of the clinical laboratory tests (full blood count, biochemical profile) will be eligible to participate in this study. Participation will occur no later than 2 weeks after clinical screening.

3.7 Preparation of tomato pomace drinks.

Tomato pomace will be processed and supplied by CEAP. In brief, chopped fresh tomatoes are heated to produce a pulp. The pulp is passed through a 'pulper' and a 'finisher' before being extracted through a turbo press to produce a pomace. The tomato pomace is concentrated to dryness by evaporation. The pomace is then extracted and dried to form a powder extract. A certificate of analysis for pesticide and microbial safety tests on the final product is provided by CEAP (annex 5).

Immediately prior to ingestion, 'drinks' containing the appropriate mass of tomato pomace extract will be prepared at the research facility as described below. The water used to dilute the extract will be flavoured using a commercially available orange flavoured powder (Kool aid) which will be diluted according to the manufacturer's instructions before adding to the tomato pomace extract. Flavoured water is necessary because this is how we intend to blind the participants to the test product in phase 2.

- 1) Low dose pomace extract 1 g extract will be accurately weighed before dissolving in flavoured water to a final mass of 100 g
- 2) Medium dose pomace extract 2.5 g extract will be accurately weighed before dissolving in flavoured water to a final mass of 100 g
- 3) High dose pomace extract 10 g extract will be accurately weighed before dissolving in flavoured water to a final mass of 100g

3.8 Intervention procedure

Participants may maintain normal dietary habits during the 5-day intervention period but will be instructed to refrain from drinking any alcohol. The format for phase 1 is intended to reflect the phase 2 study and is described below.

Week 1: 5 participants will start on the lowest dose of tomato pomace extract being tested (1.0 g). Participants will arrive at the research facility on the morning of each of the 5 treatment days after fasting from 10pm the night before. During the fasting period, the participant may drink as much water as he needs. At the start of each treatment day, the research nurse will record pulse rate and blood pressure and complete a gastro-intestinal well-being questionnaire (Annex 6). The participant will then ingest the tomato pomace extract. 3-h post ingestion of the extract, the research nurse will once again record pulse rate and blood pressure and complete another gastro-intestinal well-being questionnaire after which the participant may eat and drink as normal. The participant will then be free to leave the research facility with instructions to return the following morning to repeat the procedure. 24-h after the final treatment on day 5, another 10 mL fasted blood sample will be obtained for full blood count and biochemical assessment as described in the clinical screening section of this protocol (section 3.6).

Week 2: If no problems occur after 5-days ingestion at the lowest dose tested (see section 3.9 for criteria) then the next 5 participants will ingest the next incremental dose (2.5 g). The same procedure described for week 1 above, will be followed.

Week 3: If no problems occur in week 2 (section 3.9), then the last 5 participants will ingest the highest dose of extract (10 g). The same procedure described for week 1 above will be followed.

3.9 Stop criteria for dose escalation

Blood tests will be assessed (by a medical doctor) for abnormal variations at the end of the intervention period by comparison with the test results obtained at clinical screening. Similarly the CI will evaluate the results from the gastro-intestinal wellbeing questionnaires. Table 1 is the STOP criteria in the event that abnormal variations in blood test results and/or gastro-intestinal problems occur.

Dose extract (g)	Previous dose outcome	Abnormal at current dosing	Next step	Abnormal at re-test	Next step
		$\leq 2^{(a)}$	Escalate to next dose	n/a	n/a
1.0	N/A	≥3	Replace and re-test	0-1 ^(b)	Escalate to next dose
				≥ 2	STOP

 Table 1 Stop criteria for phase 1

Version 1 Study protocol

	All normal	≤ 2	Escalate to next dose	n/a	n/a
		≥ 3	Replace and re-test	0-1	Escalate to next dose
2.5				≥ 2	STOP
2.3	1-2 abnormal ^(a)	≤ 2	Escalate to next dose	n/a	n/a
		≥ 3	STOP	n/a	n/a
	\geq 3 abnormal ^(b)	≥2	STOP	n/a	n/a
	Any	0	Proceed to phase 2	n/a	n/a
10		1-2	Replace and re-test	0	Proceed to phase 2
				1-2	STOP
		≥3	STOP	n/a	n/a
1		1			

n/a - Not applicable; STOP - the dose-escalation study should be terminated.

If evaluation of the data indicates that the pomace extract is well tolerated at the highest dose tested, we will move onto the phase two efficacy trial.

[name] (CI) will assume responsibility for the dose escalation procedures and the decision to move into the phase two efficacy trial.

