4.1 Study hypothesis

Daily ingestion of a tomato pomace extract for 5 days will significantly reduce platelet aggregation in humans compared with a placebo control and in a dose dependent manner.

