4.7 Clinical screening

Clinical screening for this trial will be conducted as described in section 3.6. The only addition will be the assessment of platelet aggregation. This will be assessed by the research team and those participants not meeting the platelet aggregation response range defined in section 4.4 will be excluded from the trial.

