5.1 Reporting of adverse event/reactions and serious adverse events

Adverse events are defined as any undesirable experience occurring to a subject during the study, whether or not considered related to the tomato pomace extract. An **adverse reaction** is defined as all noxious and unintended responses to the tomato pomace extract related to any of the doses tested. The phrase responses to the

Version 1 Study protocol

tomato pomace extract means that a causal relationship between the product and an adverse event is at least a reasonable possibility, i.e. the relationship cannot be ruled out. All adverse events and reactions reported by the subject or observed by the Cl or his staff will be recorded (Annex 10). A serious adverse event (SAE) is defined as any untoward medical occurrence or effect that at any dose results in death, is life threatening (at the time of the event), requires hospitalization or results in persistent or significant disability or incapacity. SAE's must be reported by the Cl immediately to the University of Talca ethics committee and the study sponsor (CEAP). In this instance the trial will be immediately suspended or terminated.

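### The Phase 1 escalation rule gives no stated role to non-serious adverse events outside the gut, bleeding above all, or to the blood pressure and pulse readings

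*Combined protocol and SAP*

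**What the plan says.** On what is measured, section 3.2 states: "Tolerability of the tomato pomace ingestion will be assessed by physical measurements (blood pressure and pulse rate) and a gastro-intestinal well-being assessment". These are taken before and 3 h after each of the five daily doses. A full blood count and biochemical profile are done at screening and repeated 24 h after the last dose.

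On escalation, section 3.8 allows the second group to start on this condition: "If no problems occur after 5-days ingestion at the lowest dose tested (see section 3.9 for criteria". The third group follows on the same terms. In section 3.9 a medical doctor compares the blood tests with screening and the chief investigator (CI) evaluates the gastro-intestinal questionnaires. The scope of the rule is then given: "Table 1 is the STOP criteria in the event that abnormal variations in blood test results and/or gastro-intestinal problems occur". The CI "will assume responsibility for the dose escalation procedures and the decision to move into the phase two efficacy trial". Section 3.9 also makes Phase 2 conditional on the data showing that the top dose was tolerated well.

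On adverse events, section 5.1 covers both phases: "All adverse events and reactions reported by the subject or observed by" the CI or staff are to be recorded (Annex 10). Only a serious event has a stated consequence, namely immediate reporting and suspension or termination.

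On mechanism, section 2 says that earlier work with tomato and pomace extracts "has demonstrated marked decreases in platelet aggregation". Section 4.1 hypothesises that the extract will "significantly reduce platelet aggregation in humans compared with a placebo control and in a dose dependent manner". Platelet function is not tested in Phase 1. Comparing Phase 2 screening with section 3.6, section 4.7 says "The only addition will be the assessment of platelet aggregation".

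**The concern.** Section 3.8 makes the absence of problems the condition for the next dose, and leaves section 3.9 to say what a problem is. Section 3.9 names two kinds. A nosebleed, gum bleed, unexplained bruise, rash or faint that is not serious would be on record but is in neither category. The same holds for a marked change in blood pressure or pulse, although these readings are described as tolerability measures.

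Bleeding deserves to be named because reduced platelet aggregation is the effect the trial seeks, and Phase 1 is where the largest amount is given. At stake is the safety of the Phase 1 men: followed to the letter, the rule could move to a higher dose without anyone being required to look at such events.

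**Working it through.** The plan gives no figure on this point. Its only calculated design figure, 33 per group for Phase 2, plays no part here. The check is therefore mainly a comparison of sections.

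**1. What is collected, and what the rule uses**

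| Information | Collected under | Named in 3.9 as input to escalation? |
|---|---|---|
| Blood count and biochemistry | 3.2, 3.6, 3.8 | Yes (doctor) |
| Gastro-intestinal questionnaire | 3.2, 3.8 | Yes (CI) |
| Blood pressure and pulse | 3.2, 3.8 | No |
| Non-serious adverse events outside the gut | 5.1 | No |
| Serious adverse events | 5.1 | Not in 3.9, but they suspend or end the trial |

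**2. Whether the blood tests would stand in for a bleeding check.** Section 3.6 lists 16 biochemistry items, and none is a clotting or platelet-function test. A full blood count gives the number of platelets, not their function. A bleed large enough to change the blood count would enter Table 1; a minor one would not.

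**3. Dose.** Top Phase 1 dose over top Phase 2 dose: 10 / 2.5 = 4.

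**4. Eligibility.** Section 4.5 excludes bleeding disorders; section 3.4 does not name them. Section 3.4 does bar all medication and kidney or liver disorders, and section 3.6 requires normal laboratory results. What could remain is a mild, untreated disorder with a normal blood count and biochemistry.

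**5. Whether adding bleeds to Table 1's count would be enough.** Read the counts as men, with X ~ Binomial(5, p). At 1.0 g, and at 2.5 g after no more than two abnormal men at 1.0 g, up to two abnormal men still means escalate. The rule reacts only if X ≥ 3. The documents give no bleeding rate, so p is assumed:

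| p | P(X ≥ 3) | P(X ≥ 1) = 1 − (1 − p)^5 |
|---|---|---|
| 10% | 0.009 | 0.410 |
| 20% | 0.058 | 0.672 |
| 30% | 0.163 | 0.832 |

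So counting alone reacts weakly at the two lower doses. At 10 g the reverse holds, because one abnormal man already leads to a re-test. If unrelated events are counted in 1%, 5% or 10% of men (assumed), P(X ≥ 1) = 1 − 0.99^5, 1 − 0.95^5, 1 − 0.90^5 = 0.049, 0.226, 0.410. A separate criterion under medical review avoids both faults.

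**6. False alarms under a separate criterion.** Let r be the share of men with an unrelated event that the doctor nevertheless judges relevant. The chance of at least one such event among five men is again 0.049, 0.226 or 0.410 for r = 1%, 5% or 10%. Over all 15 men, with no re-tests, it is 1 − (1 − r)^15 = 0.140, 0.537 or 0.794.

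**The case against.** The strongest reply is that the plan leaves room to act. The CI is responsible for escalation, the CI and staff record the adverse events, and Phase 2 also requires an evaluation that the top dose was well tolerated, which is not confined to Table 1. This stands in part. It means that a sensible CI could stop for a bleed. But adverse events are not named as an input, good tolerance has no definition beyond Table 1, and the separate tolerability condition does not govern the steps from 1.0 to 2.5 g or from 2.5 to 10 g.

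It can also be said that bleeding is singled out without evidence. No section reports clinical bleeding, exposure lasts five days in healthy men aged 18 to 26, and section 4.10 treats ordinary foods as having anti-platelet activity. This too stands in part. The gap is general, which is why the fix covers all adverse events and vital signs. Bleeding is the example that follows from the trial's own hypothesis.

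Annexes 4, 6 and 10 are not available here and may already ask about bleeding or bleeding history. That makes the added questions conditional. A question on a form would still not bring the answer into section 3.9.

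A reader might infer that Table 1 would send the trial on to Phase 2 automatically even if all five men at 10 g had nosebleeds. The documents do not support that: Table 1 would count no abnormal men, but the CI's responsibility and the tolerability condition still apply.

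**Conclusion.** The concern holds as a gap in the stated escalation rule: non-serious adverse events outside the gut, and the blood pressure and pulse readings, have no stated place in it. Bleeding is the most relevant case, at up to four times the top Phase 2 dose. It is a minor safety improvement that is worth making because it is cheap.

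Three stronger inferences are not supported. The documents do not show that the extract causes bleeding: dose dependence is a hypothesis, and nothing documents the effect at 10 g. They do not show that men with a known bleeding disorder would be enrolled, given the other exclusions, the required laboratory results and the unseen health questionnaire. And nothing here weakens the Phase 2 efficacy analysis, which uses 2.5 g or less in a separate comparison.

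The conclusion rests on the body text, since the annexes are unseen. The event rates in the working are assumptions and show only how the rules would behave.

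**What to change.** 1. In section 3.9, require the medical doctor to review all recorded adverse events and the blood pressure and pulse readings before each escalation and before Phase 2. Allow a hold after a single bleeding or bruising event judged clinically relevant and not explained by injury or venepuncture. Make this a separate criterion, not only an addition to Table 1's count.
2. Add bleeding disorders to section 3.4, as in section 4.5.
3. Unless the annexes already do so, add a few questions (nose, gums, new bruises, blood in urine or stool) to the existing daily questionnaire. The Day 1 pre-dose answers serve as baseline. On Day 6, ask before the blood draw.

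On paper this is a sentence or two in 3.9, one line in 3.4 and a few lines on a form, with no added scheduled visit or sample. The real cost is the doctor's time for harmless events and an occasional unneeded hold or re-test, which could require replacement participants with their own visits and blood draws. The false-alarm figures in the working show that this cost stays low only if the doctor's review screens out most unrelated events.
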